### 3.6 Collection and Reporting of AEs, SAEs & UPs

Study participants will be instructed to contact the PI if any serious or unexpected adverse event occurs. Reported AE's will be recorded in detail in an AE case report form.

Adverse events that occur or are discussed during monitored sessions will be recorded by the study team and the PI will be notified as soon as possible. Events occurring outside of the monitored sessions or by individuals assigned to the solo cycling group will be identified by weekly calls with the participants and review of the exercise logs every four weeks. Any adverse events will be discussed at weekly research team meetings and will be reviewed to determine whether a change in protocol is necessary.

AE/SAEs that meet the definition of an unanticipated problem will be reported to the IRB within 14 business days. Events that are immediately life threatening, severely debilitating to other current subjects or resulted in a death will be reported to the IRB Chair or IRB Director via telephone or email within 24 hours (1 business day) of site awareness.

### 3.7 Protection Against Study Risks

#### Informed Consent Process

Individuals completing the phone screening will provide verbal informed consent. For those who elect to participate in the study, all participants will provide written informed consent prior to being enrolled in the full study.

#### Protection Against Risks

##### A. Steps to Minimize Risks during data collection

To minimize the risks to participants during the data collection sessions, the following risks have been identified and precautions will be taken.

- b. Physical Risks: Fatigue is the most common or frequent physical risk as some of the participants may currently be relatively sedative. Additionally, there is a possibility of a fall and injury during the assessment.
- c. Steps to Physical Risks: Fatigue: frequent breaks are schedule in the protocol. Additionally, participants will be informed that they may request a break at any time.

Falls: All participants will be closely spotted by trained study personnel during data collection sessions. Those individuals who are older or who have indicated a recent fall will be asked to wear a gait belt.

##### B. Steps to Minimize Risks during in-home exercise

To minimize the risks to participants during the exercise intervention, a number of measures and precautions will be taken. All participants will be asked during the phone screen if they have ever been told that they should not exercise or if they have any reason to believe that they should not exercise.

Each individual will complete a medical and health history form covering musculoskeletal, cardiovascular, respiratory, and other health conditions and provide a thorough list of prescription medications. If any contraindications for exercise are reported, the individual will be instructed to review the exercise protocol with their physician prior to study enrollment and provide documentation asserting that the individual is cleared for exercise. Financial assistance for a necessary screening visit to a medical provider is available. Prior to beginning all legs of the study that involve the cycling intervention, all individuals will have their maximum and target heartrate calculated and will be provided with their individual results. This table will be posted on the bike so that it is visible at all times. During scheduled exercise sessions, a study team member will monitor the participant's heart rate and perceived exertion (Borg Rating of Perceived Exertion (RPE) (Borg, 1970)) for the duration of the

session. Outside of these scheduled sessions and in the solo cycling group, participants can make use of the reference card to monitor their heartrate. Any indication of significant discomfort, exercise intolerance, a desire to stop or a medical emergency will result in termination of the session. All research staff will be familiarized with the main signs and symptoms of adverse events and will know to follow the emergency and non-emergency protocols described below.

**Physical Risk:** Common physical risks include muscle soreness, fatigue and shortness of breath. Less common physical risks include falls, heat intolerance, and skin irritation from the activity monitor. Rare but possible risks include cardio-vascular related events (sudden cardiac arrest, myocardial infarction, and stroke).

- a. Steps to decrease physical risks during exercise session –To minimize the risks of muscle soreness, we will follow appropriate guidelines for exercise by including a warm-up prior to the start of each training period, and ending with a cool-down period. We will also recommend participants keep a towel nearby and we will encourage hydration, before, during, and after exercise.
- b. To minimize excessive fatigue and shortness of breath, the intensity of the cycling session will be gradually increased and based upon the participant's previous results and anecdotal reports of fatigue before, during, and after exercise. Additionally, we will use the Borg Rating of Perceived Exertion (RPE) (Borg, 1970) and the maximum and target heartrate formulas described above to monitor participants' exercise response as well as to help individuals monitor their target and maximum heartrate values on their own throughout the sessions. Participants may terminate a session at any time.
- c. To minimize skin irritation due to the wearing of the Garmin VivoSmart activity tracker, participants will be instructed to wear the monitor snuggly, but not too tight on their preferred wrist. Participants will be told to remove the device and place it in a pocket if it cannot be donned comfortably.
- d. To minimize the risk of falls, we will utilize a customized recumbent bike, specifically fit to the individual rider, with a wider seat for more stability, handlebars on the seat, and a lower ground profile that allows participants easy entry and exit without necessitating a step over a central support. Two members of the research team will set-up the bike and properly fit it to the individual rider. Additionally, the team will ensure the stationary bike is set-up in a safe and secure manner and in an area free of clutter and dangerous obstacles.
- e. For heat intolerance, we will encourage participants to exercise in either an air-conditioned room, or in front of a fan. And as previously mentioned, the Borg Scale and HRR will be used to monitor exertion, and target heart rate intensities. Participants may terminate a session at any time.
- f. Given that the proposed intervention is an aerobic protocol, there is the risk for cardio-vascular related events (sudden cardiac arrest, myocardial infarction, and stroke). To minimize these risks, all participants will be asked if they have ever been told that they should not exercise or if they have any reason to believe that they should not exercise during the phone screen. Further, all participants will complete a medical and health history form covering musculoskeletal, cardiovascular, respiratory, and other health conditions and provide a thorough list of prescription medications. If any contraindications for exercise are reported, the individual will be instructed to review the exercise protocol with their physician prior to study enrollment and provide documentation asserting that the individual is cleared for exercise. Financial assistance for a necessary screening visit to a medical provider is available.

Age-defined heart rate targets will be calculated and each individual in all groups will be informed of their target heart rate zones. To continuously monitor HR, each participant will

don a Garmin VivoSmart 3 which provides beats per minute heartrate data and each bike includes a handlebar sensor for participants to grasp and receive a read-out of current HR. An informational sheet has been provided to instruct the participants about the use of heart rate zone calculations and perceived exertion levels (appendix V and VI). All individuals, regardless of assigned group, will be instructed to target a moderate exercise level. Moderate heart rate values are individual specific. Moderate RPE values are between 3 and 5. During monitored sessions, the research assistant will continuously monitor heart rate and will enquire about RPE at 5 minute intervals. These values will be compared to his/her target HR and RPE. **All participants will be informed that any sessions can/will be terminated by the researcher or participant at any time.**

**C. Psychosocial Risks:** Loss of confidentiality – One potential risk of participating in this study is that confidential information about the participants may be accidentally disclosed. If a participant's current diagnosis of PD is not known to others, the potential to cause damage to their psychological well-being as well as to their reputation exists.

- a. Frustration: Participants may become frustrated with the assessments as the complete battery may take up to 3 hours to complete.
- b. Embarrassment: Individuals may be embarrassed if they are unable to perform a task or if they stumble or fall during the performance of a task.
- c. Depression: As a depression screen is included in the study protocol an individual who does not know they are depressed may need to be notified. In the case of identified serious depression, the PI will notify the study participant of the potential concern and will make a recommendation for further clinical care.
- d. Suicidality: The identification of suicidal thoughts is possible due to the depression questionnaire. In the case of identified suicide risk, the study team will immediately call 911. This will compromise the confidentiality of the participant and the participant will be notified of this breach of confidentiality.
- e. *Confidentiality:* All possible care will be taken to maintain confidentiality. No subject will be identified in any report or publication. All data will be coded at the time of data collection. All participants will be assigned an identification number prior to data collection and all documents and files will be named using this ID. All data will be stored on computers which will be kept in the SMIL. All data analysis will be performed on computers in the SMIL or in the faculty office of the PI. A password is necessary for access to the computers and they all are equipped with automatic log off. Data being moved from one location to another will be moved via UW Box or the College of Education's secure network. Only members performing research have access to these computers, therefore identification of any subjects or data is unlikely. Coded data will be kept indefinitely.

Data will be stored/banked for future research projects in a double secured location. In a locked filing cabinet or a password protected computer within a locked room. Coded data will be stored on the School of Education servers indefinitely. It will be used for future research related to exercise studies in the lab. Data may be shared with researchers outside the UW. [name] will be responsible for deciding when/to whom to disseminate coded data, and will work with other researchers if necessary to confirm that they have proper IRB approval/etc., as necessary. Required UW-Madison IRB approval would be obtained prior to the release of any data.

Contact information: Each participant will have a sealed folder which contains their emergency contact information including instructions for the local 911 operator and contact information for

an identified contact person. The sealed folders marked with the participant names will be kept locked in the PI's research office. These folders are to be unsealed only in the case of an emergency. All folders and their contents will be destroyed once the individual completes the three-month follow-up or if they withdraw from the study.

Personal privacy during testing sessions will be maintained by testing in a private room and limiting the people within the research lab to current employees or students associated with the lab.

*Frustration:* To minimize the risk of frustration with the data collection sessions frequent breaks will be provided as will snacks and water during the testing sessions. Additionally, the testing sequence provides a variety of tasks to complete. If it appears that an individual is becoming frustrated with the given task, that task can be stopped or paused and a different task can be completed without disruption of the data collection session.

*Embarrassment:* The PI and her team all have experience working with individuals at an increased risk of falls. The study team will also talk with the individual to minimize the extent to which they feel embarrassed. We will minimize the likelihood of falling by using proper spotting techniques.

*Depression:* The risk associated with learning that you are depressed or suicidal based on the Beck Depression Inventory score is difficult to minimize. The study team will follow the developed protocol

## 4. Interim Analysis

An interim analysis will not be performed.

## 5. Stopping Rules

### 5.1 Participant Stopping Rules

Participants will be informed that they have the right to withdraw from the study at any time for any reason, without prejudice to their medical care. The investigator also has the right to withdraw participants from the study for any of the following reasons:

- If study intervention is discontinued due to AE
- Protocol violation
- Lost to follow-up
- Study terminated
- Non-compliance

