### **Study 2**

**SPECIFIC AIM 1:** Determine whether incorporation of social interaction during physical activity significantly improves task adherence and increases task stamina as compared to solo cycling.

**Hypothesis 1a:** Those individuals participating in socially engaged cycling will complete a significantly greater number of cycling sessions than individuals in the solo cycling group.

**Hypothesis 1b:** Individuals in the social cycling group will cycle for longer durations at each session than solo cyclists, despite the long term goal being 30 minutes per session for both groups.

**SPECIFIC AIM 2:** Determine whether incorporation of social interaction during physical activity significantly improves activities of daily living, fall rate and quantity of movement for individuals with PD. The primary variables for this aim are Performance Assessment of Self-care Skills Assessment scores, gait velocity and step count.

**Hypothesis 2a:** Socially engaged exercise will result in significantly greater improvement in measures of instrumented activities of daily living (IADL; as measured by the Performance Assessment of Self-care Skills (PASS) assessment) as compared to solo cycling.

**Hypothesis 2b:** Fall rate will be non-significantly improved with socially engaged cycling but not with solo cycling. Weekly calls will be placed to both groups to record fall rate. Falls data will allow for effect size calculations for future applications.

**Hypothesis 2c:** Overall activity level, as measured by an activity monitor, will increase with socially engaged cycling but not with solo cycling.

**Study Duration:** This study will be conducted over the next 4 years including all data analysis, manuscript and grant proposal submissions.

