For both studies, we will employ a  $2 \times 2$  repeated measures ANOVA with time and intervention as the factors, to determine the outcomes of the cycling intervention effectiveness aims. Additionally, we will use a time (posttest to 3-month follow-up) by group to examine the effectiveness of the health coach maintenance model. Variables of interest include: total number of completed sessions and session duration; PASS scores, walking velocity, stride length, base of support; gait variables (velocity, stride length, base of support and % of time in double support) and MiniBESTest scores as well as number of falls; and mean daily step count.

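### The safety plan lets the investigator withdraw Study 2 participants for undefined non-compliance although completed sessions are the Aim 1 outcome, and nothing says that withdrawn riders stay in the analysis

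*Combined protocol and SAP*

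**What the plan says.** Section 5.1 (Participant Stopping Rules) of the Data and Safety Monitoring Plan reads: "The investigator also has the right to withdraw participants from the study for any of the following reasons". The list that follows includes "Non-compliance". It gives no definition and no threshold, and it makes no distinction between the two studies. The plan applies to Study 2: its summary describes both studies, and section 3.6 says that events reported "by individuals assigned to the solo cycling group will be identified by weekly calls".

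Specific Aim 1 of Study 2 is to "Determine whether incorporation of social interaction during physical activity significantly improves task adherence and increases task stamina as compared to solo cycling". Hypothesis 1a predicts: "Those individuals participating in socially engaged cycling will complete a significantly greater number of cycling sessions than individuals in the solo cycling group". The section Power and Statistical Analysis lists "total number of completed sessions and session duration" among the variables of interest and names a repeated measures ANOVA for both studies. That section defines no analysis set. It has no intention-to-treat statement, no missing-data rule, and no rule for counting sessions after a withdrawal.

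**The concern.** In most trials, poor compliance is a nuisance. In Study 2 it is the quantity under test. A rule that lets the investigator end a participant's time in the study for non-compliance can therefore act on the outcome itself.

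The risk is unlikely to be equal in the two arms. Hypothesis 1a expects fewer sessions in the solo arm. Social riders cycle with a staff member, while solo sessions are self-directed with only a suggested progression, so it is less clear what non-compliance means for them. Blinding is described only for rating recorded UPDRS III and mini-BESTest performance. None is described for the investigator, who reviews the exercise logs.

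If the right were used for low session counts, there are two ways to handle the data, and both cause trouble. Leaving withdrawn riders out removes low counts and would shrink the contrast if those riders were mostly solo. Keeping a count that stops at withdrawal makes the outcome partly the investigator's decision and could widen the contrast. In both cases the withdrawn rider would lose posttest PASS and gait data and later step counts. PASS scores, gait velocity and step count are the primary variables of Study 2 Aim 2.

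**Working it through.** The documents state no adherence rate, spread or non-compliance threshold, so there is no figure to reproduce. The check has two parts.

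**1. The passages side by side.** Section 5.1 allows withdrawal from the study, not only from cycling. Study 2 Aim 1 and the variable list treat completed sessions as outcome data. No other section keeps a withdrawn rider in the analysis or invites that rider to posttest. The conflict is therefore in the text. Whether it does harm depends on how the right is used.

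**2. Illustration of size.** Inputs from the documents:
- Three sessions a week (Study 2 Intervention) over the 24 weeks of table 1: 3 × 24 = 72 sessions.
- 12 participants, paired and randomised to two groups (Research Design): 6 per arm.

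Assumed inputs: mean completion m, SD s, beta-distributed completion, and a cut c below which everyone is withdrawn and excluded.

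Formulas:
- k = m(1 − m)/s² − 1, a = mk, b = (1 − m)k.
- Share kept = S(c; a, b), where S is the beta upper-tail probability.
- Mean among those kept = m × S(c; a + 1, b) / S(c; a, b).
- Observed difference = 72 × (social mean kept − solo mean kept).

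First row worked through. Social, m = 0.80, s = 0.25: k = 0.16/0.0625 − 1 = 1.56, and the mean among those kept is 0.8526. Solo, m = 0.50, s = 0.25: k = 0.25/0.0625 − 1 = 3, and the mean among those kept is 0.6239. Difference = 72 × (0.8526 − 0.6239) = 16.5, against a true 72 × 0.30 = 21.6.

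| Means, social v solo | Cut | SD (points) | True difference | After exclusion | Reduction | Removed, social / solo |
|---|---|---|---|---|---|---|
| 80% v 50% | 33% | 25 | 21.6 | 16.5 | 24% | 8% / 29% |
| 80% v 50% | 33% | 15 | 21.6 | 19.1 | 12% | 1% / 14% |
| 80% v 60% | 33% | 25 | 14.4 | 12.2 | 15% | 8% / 17% |
| 80% v 60% | 33% | 15 | 14.4 | 13.6 | 6% | 1% / 4% |
| 80% v 50% | 50% | 25 | 21.6 | 12.6 | 42% | 15% / 50% |
| 80% v 50% | 50% | 15 | 21.6 | 14.2 | 34% | 5% / 50% |

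With 80% v 70%, SD 25 and the 33% cut, 7.2 becomes 6.7.

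For 80% v 50% and the 33% cut, the chance that at least one of six solo riders falls below the cut is 1 − 0.71⁶ = 87% at SD 25, and 1 − 0.86⁶, about 59%, at SD 15.

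For the other handling, a rider withdrawn at the end of week 12 can have completed at most 3 × 12 = 36 of 72 scheduled sessions. One such rider can lower the mean of a six-person arm by up to 36/6 = 6 sessions compared with riding on to the end. This is an upper bound.

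**The case against.** The strongest reply is that section 5.1 gives a right, not a duty. A reader might infer that the rule itself makes missing data depend on outcome and arm, or leaves the function outcomes estimated in compliers only. The documents do not support that. It would follow only if the investigator used the right for low session counts and the data were then lost, and neither is stated.

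Second, non-compliance is not defined as missing sessions. Participants are also asked to wear the monitor, keep the journal, start no new exercise programme and create no new device account. Reading the term as low session counts is plausible but remains an inference.

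Third, nothing says that a withdrawn participant's data are discarded. Cycling-account and monitor data are downloaded and logged weekly, so sessions and steps up to withdrawal would exist. The payment schedule also anticipates partial completion. Only later data would be lost.

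Fourth, the size rests wholly on assumed inputs, and the study is a declared pilot without power for its outcomes. With 6 per arm and an SD of 25 points (0.25 × 72 = 18 sessions), the 95% half-width for the difference is 2.228 × 18 × √(2/6) = 23 sessions, well above the shifts in the table.

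The first three points stand and limit the claim to what could happen. The fourth stands as to precision, but it does not remove the problem. Sampling error is expected in a pilot and can be reported with the estimate, whereas a selective exclusion is systematic and would not show in the interval. The plan also says that future proposals would ideally be powered from pilot data on these aims, so a distorted adherence effect could be carried forward.

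**Conclusion.** The concern holds as a conflict between a permission and an outcome. The safety plan allows withdrawal from the study for undefined non-compliance, Study 2 Aim 1 measures adherence by completed sessions, and no text keeps withdrawn riders in the analysis or at posttest. If the right were used for low session counts, the adherence contrast could be biased in either direction and Aim 2 data would be lost.

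Under exclusion, the illustrated shrinkage runs from 6% to 42% over the tabulated cases. That range assumes beta-distributed completion, the stated means, SDs and cuts, and that everyone below the cut is withdrawn, which a discretionary rule does not require. It shows what could happen and does not predict it.

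A reader might also infer that non-compliance and protocol violation should be struck from the safety plan. The argument does not reach that far. The plan is shared with Study 1, and protocol violation is undefined and could cover eligibility or safety breaches unrelated to session counts.

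**What to change.** The study team should reconcile section 5.1 with Study 2 Aim 1 and the variable list in Power and Statistical Analysis, for Study 2 only:

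- State that missed or stopped cycling sessions are outcome data and not in themselves grounds for withdrawal from the study.
- State that such participants stay enrolled and are invited to the planned posttest and 3-month follow-up.
- Analyse all randomised participants in their assigned group.
- Count completed sessions over the full planned period, with sessions not done counted as not completed.
- Report withdrawals by arm and reason.

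The adverse-event and protocol-violation grounds and the participant's own right to withdraw stay unchanged. The cost is a short wording change in the safety plan and the analysis section, and a small effort to bring non-adherent participants to visits already planned.

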All data will be coded at the time of data collection. All participants will be assigned an identification number prior to data collection and all documents and files will be named using this ID. All data will be stored on computers which will be kept in the SMIL during data collection and transferred to the School of Education's secure server either via an Ethernet connection or through UW Box. All data analysis will be performed on computers in the SMIL or in the faculty office of the PI. A password is necessary for access to the computers and they all are equipped with automatic log off. Data being moved from one location to another will be moved via UW Box or the School of Education's secure network. Access to these computers are limited to SMIL staff, therefore identification of any subjects or data is unlikely. Coded data will be kept indefinitely.

**Monitoring Software:** Activity tracker and Ride Social accounts will be established with dummy identifiers (SMIL1, SMIL2). The only link that will exist between the individual's identifiers and the accounts will be on the participant code document. Data will be downloaded from the web accounts weekly and logged in the participants data file. The only concern that currently exists is if the individual attempts to reset or create their own account for either tool and discloses their personal information. Individuals will be instructed at the beginning of the study that an account has been made for them and they should not attempt to make a new account.

**Video Data:** All video data will be stored on the School of Education server in a directory designated to the SMIL lab. Only specified lab personnel have access to the network server directory. The server is maintained by the School of Education and is backed-up nightly. Dartfish video analysis software will be used to obscure facial features of participants.

**Contact information:** Each participant will have a sealed folder which contains their emergency contact information including instructions for the local 911 operator and contact information for an identified contact person. The sealed folders marked with the participant names will be kept locked in the PI's research office. These folders are to be unsealed only in the case of an emergency. All folders and their contents will be destroyed once the individual completes the three-month follow-up or if they withdraw from the study.

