### **Participant Renumeration**

At the conclusion of the study, participants will be offered the option of keeping the bike and tablet or returning the bike and tablet and receiving \$400. All participants will be allowed to keep the VívoSmart 3 they were given at the beginning of the study. If the individual was also asked to participate in the normal care control wait-list group they will be eligible for an additional \$50.

The prorated payment schedule for those not in a wait-list group:

Baseline assessment only - \$50

Baseline assessment plus 2 months –\$100

Baseline assessment plus 4 month – \$200

Baseline assessment plus 6 month – \$300

Baseline, 6 months and posttest – Fitbit + \$300

Baseline, 6 months exercise, posttest and 3-mo follow-up - \$400 + VívoSmart 3 or  
Bike, tablet and VívoSmart 3

The prorated payment schedule for wait-list group:

Initial assessment only - \$50

Initial and baseline assessment - \$100

Initial and baseline assessment plus 2 months - \$150

Initial and baseline assessment plus 4 month - \$250

Initial and baseline assessment plus 6 month - \$350

Initial and baseline assessment, 6 months and posttest - VívoSmart 3 + \$350

Initial and baseline assessment, 6 months exercise, posttest and 3-mo follow-up - \$450 + VívoSmart 3 or  
Bike, tablet and VívoSmart 3  
+ \$50.

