#### 3.2 Adverse Event (AE) Definition

Adverse event (AE) means any untoward or unfavorable medical occurrence in a human subject or others that happens during or after participation in a research study.

An abnormal heartrate, perceived exertion rating, fall or other data point will not be assessed as an AE unless that value leads to therapeutic intervention, emergency medical service or is considered by the investigator to be a clinically significant change from baseline. These AEs will be entered into the study database.

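### Stopping cycling for an adverse event is a ground for withdrawal from the study, and no assessment is planned after early stopping, so posttest outcomes can be lost selectively

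*Combined protocol and SAP*

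**What the plan says.** **Withdrawal.** In the Data and Safety Monitoring Plan (Appendix IV), section 5.1 Participant Stopping Rules reads: "The investigator also has the right to withdraw participants from the study for any of the following reasons". The list opens with "If study intervention is discontinued due to AE". The withdrawal is from the study, not only from the bike. It is a right of the investigator, not a duty.

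**Assessments.** The Posttest assessment and 3-month follow-up assessment sections of both studies list the measures but do not mention people who stopped early. Study 1 Intervention places the posttest within one week of the last calendar day of the intervention. For an early stopper, that could mean the day cycling stopped or the planned end. Study 1 cyclists have their falls check at the first session of each week, so its occasion disappears when sessions stop.

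**Payment.** Under Participant Renumeration, the partial tiers, such as "Baseline assessment plus 2 months", carry no posttest. The first tiers with one are "Baseline, 6 months and posttest" and, for the wait-list group, "Initial and baseline assessment, 6 months and posttest". The follow-up tiers go further and refer to six months of exercise.

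**Analysis.** Power and Statistical Analysis plans a 2 × 2 repeated measures ANOVA (time by intervention) and expects attrition of about 15–20%. It names no analysis set and no missing-data method. It also says that Study 1 is meant to supply an effect size for the next proposal.

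**The concern.** Stopping a treatment and leaving a trial are different events, and 5.1 lets the first lead to the second. Someone who stops cycling after an adverse event is unlikely to be a random member of the arm. If such people lack a posttest, a repeated measures ANOVA in its usual form omits them, and the arm is represented by those who could carry on.

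During Study 1's six-month comparison a normal-care control has no intervention to discontinue, so this exit is open to one arm only. The likely direction favours cycling, and the quantity affected is the effect size the pilot exists to estimate. Section 3.2 brings falls into the picture: a fall counts as an adverse event when it leads to treatment or emergency care, or is judged a clinically significant change. Falls, gait and step count are all outcomes.

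**Working it through.** **1. The plan's own sample-size figure.** The guidance calculation gives 27 per group for 89% power at 0.05, with a 1 SD (0.1 m/s) difference called effect size 0.4. A one-way ANOVA with f = 0.4 and three groups of 27 gives 89.5%. The number of groups is not stated, so three is my assumption; a two-group, two-sided test at 1 SD would need 21 per group. Nothing below depends on this. Only the SD, the 0.1 m/s difference and the attrition rate are taken from that section.

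**2. What a visit pays.**

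| Step | Not wait-list | Wait-list |
|---|---|---|
| Six months, then posttest | 300 − 300 = $0 | 350 − 350 = $0 |
| Posttest, then follow-up | 400 − 300 = $100 | 450 − 350 = $100 |

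The posttest step adds only a monitor, which the opening paragraph of the same section lets every participant keep. A person who stops at two months is in a $100 tier ($150 for wait-list), and no listed tier adds a posttest to it. By contrast, a control's six-month comparison visit, labelled baseline, adds 100 − 50 = $50 and requires no exercise.

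**3. Numbers who might be lost.** Inputs are 20 per arm in Study 1, 12 people in Study 2 (6 per arm if split equally) and attrition of 15–20%.
- Study 1 cycling arm: 0.15 × 20 = 3 to 0.20 × 20 = 4.
- Study 2 overall: 0.15 × 12 = 1.8 to 0.20 × 12 = 2.4. One loss is 1/6 = 17% of an arm.

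**4. Shift in the completer mean.** Let *w* be the share of the arm lost and *δ* how much worse those people would have scored than completers. The full-arm mean is (1 − *w*)·m + *w*·(m − *δ*) = m − *wδ*, where m is the completer mean. The completer mean is therefore too high by *wδ*. With SD 0.1 m/s:

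| Share lost | δ = 0.5 SD (0.05 m/s) | δ = 1 SD (0.1 m/s) |
|---|---|---|
| 1 of 20 (0.05) | 0.0025 | 0.005 |
| 0.15 | 0.0075 | 0.015 |
| 0.20 | 0.010 | 0.020 |

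The lower two rows amount to 7.5–20% of the 0.1 m/s planning difference. The values of δ are assumptions. The result is a shift in one arm's mean. It carries over in full to the between-arm contrast only if control losses are unrelated to outcome.

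**5. Precision in Study 2.** The standard error of a difference in means, in SD units, is √(1/6 + 1/6) = 0.577 with everyone assessed and √(1/5 + 1/6) = 0.606 after one loss. That is about 5% wider.

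**The case against.** The strongest reply is that 5.1 only permits withdrawal. An investigator may keep a participant who has stopped cycling, and the posttest sections exclude nobody. That stands: outcomes can be lost, but the plan does not say that they will be. It does not answer the point, because no text says what happens to such a person and the analysis plan has no provision for their absence.

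Several stronger readings are tempting, and the documents do not support them:

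- **That those lost did worst because of cycling.** Section 3.2 defines an adverse event as "any untoward or unfavorable medical occurrence in a human subject or others that happens during or after participation in a research study". It need not be caused by cycling. Worse outcomes among those who stop are plausible, not stated.
- **That the payment table bars a posttest.** It prorates money and forbids no visit. The six months in the posttest tier can be read as calendar time; only the follow-up tier mentions exercise. Skipping the posttest also has a price, because the final tier includes it.
- **That falls and step data disappear.** Falls are logged and tracker data downloaded weekly, so everything up to the stop, including the event itself, should already be held.
- **That Study 2 is biased towards social cycling.** Both arms cycle and both can be stopped. Aim 1's session counts and durations do not need a posttest.
- **That every exit in Study 1 is one-sided.** Only the adverse-event ground is. Voluntary withdrawal, loss to follow-up, protocol violation and non-compliance can apply to either arm.
- **That safety follow-up is deficient.** The emergency folder rule, "All folders and their contents will be destroyed once the individual completes the three-month follow-up or if they withdraw from the study", stands as a confidentiality measure. The protocol also has follow-up calls after a session that goes badly, and weekly adverse-event review. I make no point on either.

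**Conclusion.** The point holds as a gap that permits selective loss of outcomes. Posttest gait, PASS and mini-BESTest results, and falls and step counts after the stop, are exposed. In Study 1's comparison period the adverse-event ground can act on the cycling arm alone, which may favour cycling. In Study 2 it costs precision, with no known direction of bias.

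The 0.0075–0.020 m/s shift is an upper scenario, not a forecast. It assigns all attrition in the cycling arm to early stopping and assumes a deficit of 0.5–1 SD. The plan gives no rate of stopping for adverse events, and its attrition figure appears beside guidance for a future trial. A single such loss among 20 would shift the mean by 0.0025–0.005 m/s under the same deficits. The effect may be small, but it falls on the quantity the pilot is meant to deliver and is cheap to prevent.

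**What to change.** **In 5.1**, separate discontinuing cycling from leaving the study. Suggested content: a participant whose cycling is stopped remains enrolled unless they withdraw consent or the investigator judges assessment unsafe. They keep the activity monitor and the weekly falls contact, in the form already used for controls. They are invited to the posttest and 3-month assessments on the dates originally scheduled.

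**In Power and Statistical Analysis**, state that these participants are analysed in their randomised arm.

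**In Participant Renumeration**, state that the six months in the posttest and follow-up tiers is calendar time, so that attending those visits is paid whether or not cycling continued.

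The decision on when cycling stops, and the clinical management of adverse events, are left unchanged.

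**Cost.** A wording amendment with IRB approval, plus a few extra visits, calls and payments. Even if all attrition were early stopping, this would concern 0.15 × 40 = 6 to 0.20 × 40 = 8 people in Study 1, counting controls after crossover, and about 2 in Study 2. Someone who attends both visits after stopping very early would cost up to $350 more in cash (400 − 50, or 450 − 100 for wait-list). The clarification loosens the link between payment and continued cycling. It does so under the same terms for both Study 2 arms, but session count is an outcome there, so the team should accept this knowingly. The change will not recover people who withdraw consent or cannot be reached.
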